15.0 Withdrawal of Participants

15.1 Withdrawal from the research without participant consent.

Participants will be withdrawn from the study without their consent if they are found to have diminished capacity to consent to ongoing participation, or if, in the judgment of the lead investigators, continued participation would not be in the best interest of the participant (i.e., if participation is causing distress or dysregulation in the participant). Participants may also be withdrawn from the study without consent if they are no longer willing or able to fulfill their responsibilities as study participants.

15.2 Orderly termination.

For patients in the medical records review portion of the study, termination will simply entail excluding records from withdrawn participants in CRDS reports and/or outreach efforts. For patients who consent to the CET, termination will be accomplished by cessation of all proactive outbound communications to the participant and by not fulfilling medication or treatment requests that are deemed not in the patient's best interests (e.g., if a patient has developed a contraindication to a study medication). For participants who consent to qualitative interviews, termination will mean ending

PROTOCOL TITLE: Comparative Effectiveness Trial of Tobacco Cessation Treatments among Cancer Patients who Smoke

the interview early and may also involve referrals to supportive care resources, as needed.

15.3 Withdrawal procedures.

Participants who withdraw from the medical records portion of the study and opt out of tobacco treatment outreach will have this change of status noted in both the REDCap project that guides outreach activities and CET recruitment, and in OnCore (to prevent inclusion in future CRDS reports). Participants who withdraw from the CET will have this status change noted in the REDCap project that study team members use to guide communication, treatment, and assessment activities in the CET.

Previously collected data from people who consent to the CET and later request to withdraw will be retained in study datasets, in keeping with HRP-314 criteria for approval for FDA-regulated research. Removal will not be possible once deidentification has occurred; it will not be possible to identify and delete records for specific participants.

Participants who are incarcerated during the study or who request temporary suspensions of outreach, treatment, or communication will be given a temporary suspension status until they are able to resume participation because their incarceration or inability to participate has ended (e.g., they have been released or transitioned to parole or probation).

Patients withdrawn from the due to safety risk related to their health or wellbeing will be notified by the research team and advised if any safety procedures are recommended. This will be documented in study records, and adverse and serious adverse event reporting guidelines will be followed.

People who choose to withdraw during the qualitative interview will have the option to request that none of the information they shared will be used in the study. In that case, the interview recording will be destroyed and no transcript will be created.

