4.0 Number of Participants

4.1 Total number of participants to be accrued. Up to 82 adult participants will be enrolled in the clinical trial by UW-CTRI staff from UW Carbon Cancer Center clinic referrals over 12-30 months. We will continue enrolling within each clinic until we reach saturation in qualitative data analysis of patient interviews (maximum N=32) and until we reach our target enrollment for the CET (N=50).

4.2 Number of participants needed to complete the research procedures. We anticipate that we will engage 12% of participants in some form of evidence-based treatment, and that 50 will enroll in the proposed comparative effectiveness study while another 50 will opt for the Wisconsin Tobacco Quit Line. As such, we anticipate that we will need to reach out to approximately 833 patients who meet criteria to be included on the quarterly CRDS reports that will guide proactive outreach letters and calls. We anticipate that the remaining 733 participants will either opt-out of smoking treatment outreach, will not be reached by the outreach team, will decline tobacco treatment, will elect to pursue treatment via their primary care provider or other means (e.g., over-the-counter) rather than to use formal treatment, or will not complete the treatment enrollment process for other reasons.

Among the 50 participants who enroll in the CET, we will use an intent-to-treat approach to data analyses so that all randomized participants will be included in key analyses of feasibility, acceptability, and abstinence rates, even if lost to follow-up. In primary analyses of abstinence outcomes, missing cases will be treated as still smoking. This will be supplemented by sensitivity analyses under varying assumptions regarding censored data (i.e., that 5%, 10%, or 20% of missing data are abstinent).

For the qualitative interviews, even 2-5 interviews could inform and enhance study methods. We anticipate that we could reach thematic saturation in qualitative data coding with fewer than 32 interviews, and have set 32 as an upper limit for recruitment.

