Follow-up assessments. UW-CTRI follow-up assessors will call CET participants 12 and 26 weeks after their target quit dates to collect outcome data (see uploaded follow-up surveys) including: tobacco use; quitting motivation and confidence; stress, mood, wellbeing, quality of life, support, and symptom burden; and treatment utilization, satisfaction, and adverse events. In addition to these self-report measures, counseling utilization and medication refill data will be used to track smoking treatment adherence; EHR data on healthcare utilization and diagnoses will be extracted (with patient consent provided at enrollment); and biochemical verification of abstinence claims at the 6-months post-quit follow-up

PROTOCOL TITLE: Comparative Effectiveness Trial of Tobacco Cessation Treatments among Cancer Patients who Smoke

will be obtained via carbon monoxide breath samples and urinary cotinine samples, or mailed saliva samples (as participants are able to provide them).

13.2 CET procedure schedule.

Study Phase	Enroll- ment	Treatment/Intervention Calls								Follow Up Calls	FU Visit
Study Contact	1	2	3	4	5	6	7	8	9	10	11
Week relative to target quit day (tqd, day 0)	-8 to -3	-1	0 tqd	1	2	4	8	12	12	26	26-29
Eligibility screening	✓										
Oral informed consent & HIPAA Authorization	✓										
Clinician(s) given 5 business days to disapprove study medication; medications dispensed if not disapproved	✓										
Tobacco, alcohol, and cannabis history	✓										
Nicotine dependence	✓										
Motivation to quit	✓	✓	✓	✓					✓	✓	
Quitting confidence	✓	✓	✓	✓					✓	✓	
Stress, mood, and withdrawal		✓	✓	✓					✓	✓	
Wellbeing and quality of life	✓								✓	✓	
Social support	✓								✓	✓	
Demographics	✓										
Randomization	✓										
Welcome mailing packet with study information sheet sent	✓										
Standard care (SC) counseling (10-15 minutes)		SC	SC	SC							
Standard care nicotine patch treatment (2 weeks)			SC	SC							
Enhanced care (EC), cancer-specific counseling		EC	EC	EC	EC	EC	EC	EC			
Enhanced care varenicline treatment (12 weeks)		EC	EC	EC	EC	EC	EC	EC			

PROTOCOL TITLE: Comparative Effectiveness Trial of Tobacco Cessation Treatments among Cancer Patients who Smoke

beginning with run-in period 1 week pre-quit followed by 11 weeks at full dose post-quit, as per package insert)										
Recent tobacco, alcohol, and cannabis use								✓	✓	✓
Treatment use								✓	✓	✓
Treatment satisfaction								✓	✓	

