The only biospecimens to be collected in the study will be collected directly from CET participants at the follow-up visit 6 months after a participant's target quit date, if the participant reported no use of tobacco products at the 26-week post-quit-date follow-up call. These participants reporting abstinence from tobacco will be asked to provide a breath sample for CO testing and a single urine sample for cotinine testing at either the UW-CTRI Madison office or at their oncology clinic (if willing to schedule this so it coincides with a clinic visit). Breath samples cannot be stored and urine samples will be tested immediately after collection and then discarded the same day. If patients are unable to travel to Madison for biochemical verification of abstinence, they will be given the option of providing a saliva sample in the mail using a kit supplied by the research team. These kits would be retained only until testing by a lab is complete and would then be destroyed.

3. Drugs.

The medications to be used in this study include transdermal nicotine patches and varenicline. Both medications are approved by the FDA for use as smoking cessation aids. No other medications or devices will be used in the research.

13.4 Data Collection.

• List of data elements.

The following data elements will be extracted from EHR data via CRDS reports. These data elements are needed to enable preparation of initial study recruitment mailings that will let patients know they have been identified for the study and that they can opt out of recruitment calls and letters.

- MRN
- Name
- Phone numbers (with preferred number flagged)
- Address
- City
- State
- ZIP code
- Communication preferences (MyChart, mail, phone)
- Tobacco use status (must be smoking currently)

PROTOCOL TITLE: Comparative Effectiveness Trial of Tobacco Cessation Treatments among Cancer Patients who Smoke

- Preferred language (must be English or missing)
 - Use of smokeless tobacco
 - Use of e-cigarettes
 - Date of birth (must be at least 18 years old)
 - Sex
 - Gender
 - Race
 - Ethnicity
 - Insurance type
 - Assigned primary care provider
 - Oncologist
 - Clinic department (where seen in the past year to achieve eligibility)
 - Cancer diagnosis (diagnosis in past 3 years that conferred eligibility)

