No formal inferential interim analyses are planned for this pilot study, but safety data will be examined on an on-going basis to determine if individual participants are at risk or if any treatment element or condition is exerting an iatrogenic effect. If any meaningful evidence of this is detected the DSMC will be consulted along with the IRB to consider study discontinuation or changes. If any danger is deemed likely and significant the study will be immediately suspended.

20.6 Handling of Missing Data. The intent-to-treat principle will be applied to primary analyses. Patients who do not initiate smoking treatment via a UW-CTRI study coordinator will be assumed to not have initiated treatment. In analyses of abstinence, cases who do not report abstinence and provide biochemical evidence of abstinence will be coded as still smoking in primary analyses. This will be supplemented by sensitivity analyses to estimate treatment effects under different assumptions regarding missing data (e.g., if 10%, 20% or 30% of people without verified abstinence are abstinent).

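### Sections 15.1–15.3 do not separate stopping study treatment from ending outcome follow-up, so a withdrawal decision can replace an obtainable 26-week outcome with the code for smoking

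*Combined protocol and SAP*

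**What the plan says.** Section 15.1 lists grounds for withdrawal without the participant's consent. Two are mandatory: diminished capacity, and a judgement by the lead investigators that continuing is not in the participant's best interest, for example because of distress. A third is discretionary: "Participants may also be withdrawn from the study without consent if they are no longer willing or able to fulfill their responsibilities" as study participants. The protocol does not say what these responsibilities are.

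Section 15.2 says that for those who consented to the trial "termination will be accomplished by cessation of all proactive outbound communications to the participant". The same sentence adds that treatment requests judged not to be in the patient's best interest will not be filled. Section 15.3 notes the withdrawn status in the REDCap project that guides communication, treatment and assessment alike, and keeps data already collected. It does not mention outcome collection after withdrawal.

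Outcomes depend on outbound contact. Section 13.1: "UW-CTRI follow-up assessors will call CET participants 12 and 26 weeks after their target quit dates to collect outcome data". Under Section 13.3, samples for biochemical verification are requested only "if the participant reported no use of tobacco products at the 26-week post-quit-date follow-up call". Section 13.3 also describes the 12- and 26-week contacts as taking place for every study participant.

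On analysis, Section 4.2 says "all randomized participants will be included in key analyses of feasibility, acceptability, and abstinence rates, even if lost to follow-up", and Section 20.6 says "cases who do not report abstinence and provide biochemical evidence of abstinence will be coded as still smoking in primary analyses".

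**The concern.** Stopping study treatment and ceasing to be measured are different events, and an intent-to-treat estimate is better protected when the second does not follow automatically from the first. Here one withdrawal step covers both. A staff decision on an undefined ground can therefore end the calls that supply the primary outcome, and the analysis rule then fills the gap with a failure. The missing outcome is avoidable in anyone who would still have answered the 26-week call.

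The pilot exists to produce an effect estimate that will guide a full-scale trial (Sections 3.1 and 20.2). With 25 participants per arm (Section 4.3), each person is 1/25 = 4 percentage points of an arm's denominator, so even a few such cases can shift the estimate if they fall unevenly between arms. The same contacts also carry adverse event assessment through week 26 (Section 13.2).

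**Working it through.** **Step 1: follow one participant through the text.**

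- The team withdraws the participant as no longer willing or able to meet responsibilities (15.1).
- All proactive outbound contact stops (15.2). No exception is made for assessors.
- The 12- and 26-week calls are outbound (13.1), so on the plain reading they are not made.
- Without a report of abstinence at the 26-week call, no sample is requested (13.3).
- Without reported and verified abstinence, the participant is coded as smoking (20.6) and is counted in the arm (4.2).

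Each link is stated. What is missing is any sentence saying whether someone who leaves treatment, but would still take a call, remains in outcome follow-up. Section 13.3's statement that the contacts occur for every participant does not mention withdrawn participants, so it does not settle the matter.

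**Step 2: the possible size.** The plan gives no withdrawal rate and no figure of its own to reproduce, so this is an illustration.

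Inputs:

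- 25 per arm, from Section 4.3.
- Assumed true abstinence *p* of 34.5% (enhanced) and 21.5% (standard). These are the results of the cited counselling trial in cancer patients in Section 2.5, borrowed here as an assumption.
- *w*, the share of an arm withdrawn before week 26 (assumed).
- *f*, the abstinence rate in the withdrawn divided by the arm rate (assumed).

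Formulas:

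- Observed rate = *p* × (1 − *w* × *f*).
- OR = [e/(1 − e)] / [c/(1 − c)], where e and c are the observed rates in enhanced and standard care.

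Worked case, 3 vs 1 withdrawn with *f* = 1:

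- Enhanced: 0.345 × 22/25 = 0.304.
- Standard: 0.215 × 24/25 = 0.206.
- OR = (0.3036/0.6964) / (0.2064/0.7936) = 1.68.

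| Withdrawn, enhanced vs standard | *f* | Observed rates | Difference (points) | OR |
|---|---|---|---|---|
| 0 vs 0 | – | 34.5% vs 21.5% | 13.0 | 1.92 |
| 3 vs 1 | 1 | 30.4% vs 20.6% | 9.7 | 1.68 |
| 3 vs 1 | 0.5 | 32.4% vs 21.1% | 11.4 | 1.80 |
| 3 vs 1 | 0 | 34.5% vs 21.5% | 13.0 | 1.92 |
| 2 vs 2 | 1 | 31.7% vs 19.8% | 12.0 | 1.89 |
| 5 vs 5 | 1 | 27.6% vs 17.2% | 10.4 | 1.84 |
| 5 vs 0 | 1 | 27.6% vs 21.5% | 6.1 | 1.39 |
| 0 vs 5 | 1 | 34.5% vs 17.2% | 17.3 | 2.54 |

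Equal withdrawal changes the odds ratio little. Unequal withdrawal can move it materially, in either direction. If the withdrawn would not have quit anyway, nothing is lost.

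**Step 3: do the planned sensitivity analyses repair this?** Section 4.2 varies the assumption "that 5%, 10%, or 20% of missing data are abstinent". Section 20.6 instead considers results "if 10%, 20% or 30% of people without verified abstinence are abstinent". The percentages differ, so does the group they apply to, and neither section states an arm-specific assumption.

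Apply Section 4.2's highest value, 20%, to the 3 vs 1 case with *f* = 1, treating these four people as the only missing cases:

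- Enhanced: 0.3036 + 0.12 × 0.20 = 0.3276.
- Standard: 0.2064 + 0.04 × 0.20 = 0.2144.
- OR = (0.3276/0.6724) / (0.2144/0.7856) = 1.79.

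That recovers part of the gap between 1.68 and 1.92, by assumption and not by measurement.

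**The case against.** A reader might infer that the withdrawal rule defeats the intent-to-treat plan. The documents do not support that. They commit to an intent-to-treat analysis that foresees loss to follow-up, keeps every randomized participant in the denominator and adds sensitivity analyses. No section explicitly promises outcome collection after withdrawal.

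A reader might also infer that poor adherence is turned into treatment failure by rule. That is too strong as well. The responsibilities are undefined and are not equated with treatment use, and the ground is discretionary. Participants who cannot have study medication stay in the trial (5.1, 6.2). Adherence and retention are themselves endpoints (3.4). Participants may decline individual activities (22.2), and Section 15.3 has a separate temporary suspension status.

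Nor do the documents show bias against enhanced care. That arm asks more of participants, with 7 calls against 3, but Sections 3.3 and 20.1 expect higher retention and adherence there.

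Finally, the illustration is small beside sampling error. At 34.5% vs 21.5% with 25 per arm, the expected cell counts are 8.625, 16.375, 5.375 and 19.625. The standard error of the log odds ratio is √(1/8.625 + 1/16.375 + 1/5.375 + 1/19.625) = 0.64, so an approximate 95% interval around 1.92 runs from 0.54 to 6.8. Section 20.2 already concedes that 50 participants are too few to test moderate benefits.

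All of this limits how much can be claimed. It does not remove the gap. The suspension status covers incarceration or a participant's own request, not team withdrawal. The right to decline single activities is not tied to remaining in follow-up. Low precision is no reason to accept a missing outcome that a phone call could prevent.

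**Conclusion.** The point holds as a gap in the withdrawal rules. Stopping treatment and ending outcome follow-up are not separated, contact stops without an exception for outcome calls, and Section 15.2 is not reconciled with Section 13.3. An obtainable 26-week outcome can therefore be replaced by the code for smoking.

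The consequence cannot be sized from the documents. It depends on how often the discretionary ground is used, how it falls between arms, and how many of the withdrawn would have been abstinent. Under the assumed rates and the assumed 3 vs 1 split, the odds ratio falls from 1.92 to between 1.68 and 1.92, depending on abstinence among the withdrawn (from the arm rate down to none). A split the other way would raise it. The planned sensitivity analyses help only in part. This is a cheap improvement worth making, not a flaw that invalidates the pilot.

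**What to change.** In Sections 15.1–15.3:

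- Define two separate events: stopping study treatment, and withdrawing from follow-up.
- Keep the 12- and 26-week calls and biochemical verification for anyone who stops or is taken off study treatment, unless the person declines further contact, has lost capacity to consent, or is withdrawn on the existing best-interest or distress ground.
- Remove failure to meet responsibilities as a reason to stop outcome collection.
- Record the type and reason of each withdrawal, and report them by arm.
- Reconcile the stop on outbound contact in 15.2 with the statement in 13.3 that follow-up contacts occur for every participant.

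The grounds for stopping treatment need not change. The cost is protocol wording, a REDCap field and a few extra calls.

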16.0 Data Management and Confidentiality

16.1 Quality control.

Both an internal quality improvement team and an external Data Safety and Monitoring Committee will help to monitor and ensure data quality. The project will follow a thorough Data and Safety Monitoring Plan (DSMP). Under this DSMP, the Lead Researcher will develop and implement protocols for assuring UW-CTRI data collection accuracy and protocol compliance, with the support of the UW-CTRI staff including the Director of Information Technology (IT) and the Regulatory and Compliance Coordinator, among others

PROTOCOL TITLE: Comparative Effectiveness Trial of Tobacco Cessation Treatments among Cancer Patients who Smoke

(e.g., our database and implementation teams and study coordinators). Study protocols will include data verification and protocol compliance checks. The Lead Researcher will also be responsible for ensuring that the data for the project are securely transferred from UW Health and securely stored at UW-CTRI, in compliance with University and federal regulations, and that no unauthorized persons have access (electronic or physical) to any participant-identifiable data. HIPAA regulations and guidelines are currently implemented at UW-CTRI, and all study staff must complete approved human subjects and HIPAA training programs. In addition, the Department of Medicine employs extensive data backup and server redundancy procedures and performs full backups weekly of all servers, along with incremental and daily backups to prevent loss of data.

16.2 Data security.

As specified in the DSMP, the Lead Researcher will be responsible for ensuring that the data for the project are securely transferred from UW Health and securely stored at UW-CTRI, in compliance with University and federal regulations, and that no unauthorized persons have access (electronic or physical) to any participant-identifiable data. HIPAA regulations and guidelines are currently implemented at UW-CTRI, and all study staff must complete approved human subjects and HIPAA training programs. Inter-site data transfers are accomplished via secure UW REDCap or file transfer protocols (SFTP) using an internet server maintained by the UW School of Medicine and Public Health (UWSMPH) Department of Medicine. To protect the privacy of database records and the integrity of the network, this server is firewall-protected and is stored in a locked server room with a numeric keypad to restrict entry. The server is continuously scanned for viruses. A complete virus scan of all workstations also takes place once a week. Server system log files are scanned for unusual activity, which is immediately investigated. Network and server administration staff members apply critical and non-critical patches as needed. In addition, UW-CTRI and UWSMPH Department of Medicine also have multiple mechanisms for preserving confidentiality of research participants and providing data security in the transfer of data from participant machines to the SFTP server. The Department of Medicine web servers use Secure Socket Layer (SSL or https) technology to encrypt data exchanged between the client and the server. In addition, all online and offline components of data systems will be accessible only through a login and password unique to each user. The security access levels for these login accounts are tiered and the features and privileges given to each staff member will be determined by the PI and UW-CTRI Director of Information Technology (IT). To further protect confidentiality, only the UW-CTRI Director of IT will be permitted to transmit data to the SFTP server. Additional measures include:

PROTOCOL TITLE: Comparative Effectiveness Trial of Tobacco Cessation Treatments among Cancer Patients who Smoke

- Data will be coded, and the “key” linking identities to codes will be kept separately from the data.
- Data will be coded, and the “key” linking identities to codes will be kept on paper only. The study data will be stored electronically and labeled only with codes.
- Only those listed as key personnel will have access to the “key.”
- Access to the “key” will be limited to the following people (e.g., Database Administrator): Database Administrators, Saliva Sample Collection Coordinator.
- This study is funded by the National Institutes of Health and is covered by a Certificate of Confidentiality.
- This study is NOT funded by the National Institutes of Health but because it will collect sensitive information, the research team will apply for a Certificate of Confidentiality to protect data from being requested without the subject’s consent as part of a legal proceeding.
- Other: _____

A unique study ID will be used to store all data on individual participants and information linking that study ID to participant identifying information will be accessible only to Database Administrators. Data being used for analysis will be identified with the study ID only. Participant contact information will only be available to study staff having direct contact with participants, and only when needed to complete such contacts, as per protocol.

For qualitative interview data, a random ID will be assigned to each transcript, and all transcripts will be thoroughly deidentified.

If a saliva sample is needed from a participant, a separate unique identifying code will be used to label the saliva collection kit. Only the person coordinating saliva sample data collection will have the key to that code.

Participant study data will be collected by UW-CTRI research personnel through REDCap and will be stored on secure, password protected servers. Data will be accessible only to assigned study staff for their study function; computer workstations will be password-protected, and thus secured from unauthorized use. Healthcare systems will transmit identifying information to UW-CTRI via secure, HIPAA compliant means. A Certificate of Confidentiality will be issued for the study.

16.3 Data storage:

- Online Collaborative Research Environment (OnCore) Biospecimen Management
- Research Electronic Data Capture (REDCap) *Specify which instance you will be using (e.g., ICTR's, Department of Medicine's): UW-CTRI Instance*
- Other software option that will be stored on departmental server. *Specify the department: UW-CTRI*
- Locked filing cabinet or drawer inside a locked room. *Specify the building: _____*
- Other (describe): Saliva samples returned via mail by participants will be stored in a locked cabinet in a locked office until ready to be shipped to a lab for testing. Samples will be identified by a code number only.
- Data will not be stored or accessed on portable devices.
- Portable devices such as laptops will be used to access secure web-based data collection sites such as REDCap. No data will be stored locally on the devices.
- Data stored on portable devices will be coded with the key stored separately. No identifiers will be stored on portable devices.
- Data stored on portable devices and therefore only encrypted devices will be used.

16.4 Management of Identifiers:

- Identifiers will be destroyed after all data has been collected.
- Identifiers will be destroyed at study closure.
- Identifiers will be destroyed at study closure or at the time of publication.

16.5 Data and specimen handling:

1. Data associated with specimens.

A subset of participants in the CET who report no smoking in the past 7 days 26 weeks after their target date to quit smoking and who are unable to come to Madison to provide a breath and urine sample for biochemical verification of abstinence will be sent saliva collection kits identified by a unique code number specific to saliva tests kits. These kits will include instructions for home collection of saliva using the passive drool method, collection materials, and a stamped, addressed return envelope to return samples to the study team. Only the team member

PROTOCOL TITLE: Comparative Effectiveness Trial of Tobacco Cessation Treatments among Cancer Patients who Smoke

coordinating saliva sample collection will have the key to this code, and they will be responsible for entering results from the saliva testing in the REDCap database. This unique key will be destroyed on study closure. No other biospecimens (breath or urine samples) will be banked. These samples will instead be tested immediately and recorded in the REDCap database.

2. **Where and how data or specimens will be stored.**
Saliva samples will be stored in a locked cabinet in a locked office until ready to ship to the lab that conducts the testing and returns results identified only by the unique sample identifier to the saliva collection coordinator for the study.
3. **How long will the data or specimens will be stored.**
Saliva samples will be stored until ready to ship to the testing lab (within 3 weeks of sample collection). The samples will be destroyed by the testing lab after testing is complete and a study team member has received testing results via a secure portal maintained by the lab.
4. **Who will have access to the data or specimens.**
The Lead Researcher will designate a Research Manager to serve as the Saliva Sample Collection Coordinator for this project. This person will be the only one to have access to the samples, and will be responsible for transcribing the results into the REDCap project. The Lead Researcher will serve as backup to this Coordinator if he/she is unable to fulfill these duties.
5. **Who is responsible for receipt and transmission of the data or specimens.**
The Lead Researcher and the Research Manager designated to serve as the Saliva Sample Collection Coordinator will be responsible for receipt and transmission of data or specimens, and transcription of results in REDCap.
6. **How data or specimens will be transported.**
The saliva sample collection kit is designed to collect and store samples at room temperature for up to 23 days. As such, regular mail or shipping methods (e.g., USPS, UPS, FedEx) will be used to transport specimens.

16.6 Sharing of data or specimens.

1. What data and/or specimens will be shared.

No specimens will be shared with those outside the research team and testing laboratory. Self-report data, treatment utilization data, and biochemically confirmed abstinence data will be shared with other researchers in a fully deidentified manner via the BioLINCC repository (rather than directly to other researchers), under approved and fully executed data use

PROTOCOL TITLE: Comparative Effectiveness Trial of Tobacco Cessation Treatments among Cancer Patients who Smoke

agreements (the BioLINCC RMDA), in accordance with the policy on resource sharing at NIH, the funder of this research.

2. Identifiers.

Data shared will be stripped of all identifiers and assigned a random ID code rather than remaining linked to participant identifiers in any way.

3. Transmission. Data transfers will occur via secure means (e.g., SFTP, secure BOX) in accordance with University policy.

4. The study will NOT share large-scale genomic data.

5. Repository.

The study will use the BioLINCC repository.

6. Limitations on the sharing of data.

Data will be shared with controlled access in BioLINCC for general research use, as allowed by the participant's informed consent and Institutional Certification.. We will submit a future change of protocol to request Institutional Certification when we have draft materials (e.g., data dictionaries, explanation of coded variables) ready for submission to the BioLINCC repository.

